### **6.3.1.1. Incidence of Adverse Events**

An overall summary of unsolicited TEAEs including the number and percentage of subjects who experience the following will be presented:

- Any unsolicited TEAEs
- Any serious TEAEs
- Any fatal TEAEs
- Any unsolicited medically-attended TEAEs
- Any unsolicited TEAEs leading to discontinuation from study vaccine
- Any unsolicited TEAEs leading to discontinuation from participation in the study
- Any unsolicited severe TEAEs
- Any AESI of MIS-C
- Any AESI other than MIS-C

The table will also include number and percentage of subjects with unsolicited TEAEs that are treatment-related in each of the above categories.

In addition, separate listings containing individual subject adverse event data for unsolicited AEs, unsolicited TEAEs leading to discontinuation from study vaccine, unsolicited TEAEs leading to discontinuation from participation in the study, serious AEs, unsolicited medically-attended AEs, AESI of MIS-C, and AESI other than MIS-C (including myocarditis and/or pericarditis) will be provided separately.

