### 3. Study Endpoints

#### 3.1. Primary Endpoints

The primary safety objective will be evaluated by the following safety endpoints:

- Solicited local and systemic adverse reactions (ARs) through 7 days after each injection.
- Unsolicited adverse events (AEs) through 28 days after each injection.
- Medically-attended AEs (MAAEs) through the entire study period.
- Serious AEs (SAEs) through the entire study period.
- AE of special interest (AESI) of multisystem inflammatory syndrome in children (MIS-C) through the entire study period.
- Vital sign measurements.
- Physical examination findings.

The primary immunogenicity objective will be evaluated by either:

- The proportion of participants with a serum Ab level at Day 57  $\geq$  an Ab threshold of protection. If an accepted serum Ab threshold of vaccine protection against COVID-19 is available, this analysis will form the basis to infer efficacy.
- The primary vaccine response as measured by GM value of serum antibody level and seroresponse rate from Study P203 vaccine recipients at Day 57 compared with those obtained from young adult vaccine recipients (18-25 years of age) at Day 57 in the clinical endpoint efficacy trial (Study P301). If a threshold of protection is not available, efficacy will be inferred based on establishing noninferiority of adolescent (12 to  $<$  18 years; this clinical study) to adult GM values of serum

antibody level and seroresponse rate obtained in Study P301 (GM value 12 to < 18 years / GM value 18-25 years).

Seroresponse due to vaccination at a subject level may be defined as a change from below the LLOQ to equal to or above  $4 \times$ LLOQ, or a 4-fold rise if baseline is equal to or above LLOQ.

Among the two Pseudovirus tests, PsVNT50 and PsVNT80, PsVNT50 is considered the most appropriate measure of subject response because it falls in the middle of the dynamic range of the dilution response curve while PsVNT80 is close to the plateau and thus subject to restriction.

The GM and seroresponse rate comparisons between adolescents in P203 and young adults (18-25 years of age) in P301 will be compared for the bAb and nAb measures, with pseudovirus nAb PsVNT50 (ID50) considered as the primary assay test for the immunobridging.

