### **6.3.1. Adverse Events**

A treatment-emergent AE (TEAE) is defined as any event occurring during the study not before exposure to study vaccine or any event already present that worsens after exposure to study vaccine. [Note: worsening of a pre-existing condition after vaccination will be reported as a new AE.]

Adverse events will also be evaluated by the investigator for the coexistence of MAAE which is defined as an AE that leads to an unscheduled visit to a healthcare practitioner.

Unsolicited AEs will be coded by PT and SOC using MedDRA and summarized by vaccination group, and stage (up to 28 days after any vaccination and overall stage; see [Section 6.1](#) for definitions of vaccination group and stage).

All summary tables (except for the overall summary of AEs) for unsolicited AEs will be presented by SOC and PT for TEAEs with numbers of subjects included. SOC will be displayed in internationally agreed order. PT will be displayed in descending order of frequency of mRNA-1273 and then alphabetically within SOC. When summarizing the

number and percentage of subjects with an event, subjects with multiple occurrences of the same AE or a continuing AE will be counted once. Subjects will be presented according to the highest severity (the strongest relationship) in the summaries by severity (of related AEs), if subjects reported multiple events under the same SOC and/or PT.

Percentages will be based upon the number of subjects in the Safety Set within each vaccination group.

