### **6.3.1.2. TEAEs by System Organ Class and Preferred Term**

The following summary tables of TEAEs will be provided by SOC and PT using frequency counts and percentages (i.e., number and percentage of subjects with an event):

- All unsolicited TEAEs
- All unsolicited TEAEs that are treatment-related
- All serious TEAEs
- All serious TEAEs that are treatment-related
- All unsolicited TEAEs leading to discontinuation from study vaccine
- All unsolicited TEAEs leading to discontinuation from participation in the study
- All unsolicited Severe TEAEs
- All unsolicited Severe TEAEs that are treatment-related
- All unsolicited medically-attended TEAEs
- All unsolicited medically-attended TEAEs that are treatment-related
- All AESI of MIS-C
- All AESI other than MIS-C

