#### **6.3.2. Solicited Adverse Reactions**

An AR is any AE for which there is a reasonable possibility that the test product caused the AE. The term “Solicited Adverse Reactions” refers to selected signs and symptoms occurring after injection administration during a specified post-injection follow-up period (day of injection and 6 subsequent days). The solicited ARs are recorded by the subject in eDiary. The occurrence and intensity of selected signs and symptoms is actively solicited

from the participant during a specified post-injection follow-up period (day of injection and 6 subsequent days), using a pre-defined checklist (i.e., solicited ARs).

The following local ARs will be solicited by the eDiary: pain at injection site, erythema (redness) at injection site, swelling (hardness) at injection site, and localized axillary swelling or tenderness ipsilateral to the injection arm.

The following systemic ARs will be solicited by the eDiary: headache, fatigue, myalgia (muscle aches all over the body), arthralgia (aching in several joints), nausea/vomiting, rash, fever, and chills.

The solicited ARs will be graded based on the grading scales presented in [Table 6 in the protocol](#), modified from the Toxicity Grading Scale for Healthy Adult and Adolescent Volunteers Enrolled in Preventative Vaccine Clinical Trials (DHHS 2007). Investigator will assess Grade 4 events (with exception of fever).

If a solicited local or systemic AR continues beyond 7 days post injection, the participant will be prompted to capture the solicited local or systemic AR in the eDiary until resolution.

All solicited ARs (local and systemic) will be considered causally related to injection.

Analyses of solicited ARs will be provided by treatment group for each injection (first or second) based on the associated subset of Solicited Safety Set, i.e. First (Second) Injection Solicited Safety Set; and for any injection based on the Solicited Safety Set, unless otherwise specified.

The number and percentage of subjects who reported each individual solicited local AR (has a severity grade of Grade 1 or greater) and solicited systemic AR (has a severity grade of Grade 1 or greater) during the 7-day follow-up period after each injection will be tabulated by vaccination group, severity grade, and injection. The number and percentage of subjects who reported each individual solicited AR will also be summarized by vaccination group, severity grade, days of reporting and injection.

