11. An unscheduled visit may be prompted by reactogenicity issues, illness visit criteria for COVID-19, or new or ongoing AEs. If a participant meets the prespecified criteria of suspicion for COVID-19 (Section 7.1.6), the participants will be asked to return within 72 hours or as soon as possible to the study site for an unscheduled illness visit, to include an NP or nasal swab sample (for RT-PCR testing) and other clinical evaluations. If a study site visit is not possible, a home visit may be arranged to collect the NP or nasal sample and conduct clinical evaluations. If a home visit is not possible, the participant will be asked to submit a saliva sample to the study site by a Sponsor-approved method. At this illness visit, the NP or nasal swab samples will be collected to evaluate for the presence of SARS-CoV-2 infection. NP or nasal swab samples will also be tested for the presence of other respiratory pathogens. If due to COVID-19 related restrictions in the community, the participant's LAR performed a home test rather than obtaining a test performed by a health care professional, see Section 7.1.6. In addition, the study site may collect an additional NP or nasal sample for SARS-CoV-2 testing to be able to render appropriate medical care for the study participant as determined by local standards of care. Additionally, clinical information will be carefully collected to evaluate the severity of the clinical care.
12. A convalescent visit will be scheduled approximately 28 days (+7 days) after diagnosis. At this visit, an NP or nasal swab sampling for viral PCR and a blood sample will be collected for potential immunologic assessment of SARS-CoV-2 infection.

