### **6.3.2. Solicited Adverse Reactions**

An AR is any AE for which there is a reasonable possibility that the test product caused the AE. The term “Solicited Adverse Reactions” refers to selected signs and symptoms occurring after injection administration during a specified post-injection follow-up period (day of injection and 6 subsequent days). The solicited ARs are recorded by the subject in eDiary. The occurrence and intensity of selected signs and symptoms is actively solicited from the participant during a specified post-injection follow-up period (day of injection and 6 subsequent days), using a pre-defined checklist (i.e., solicited ARs).

The following local ARs will be solicited by the eDiary in each part except Part 1B: pain at injection site, erythema (redness) at injection site, swelling (hardness) at injection site, and localized axillary swelling or tenderness ipsilateral to the injection arm.

The following systemic ARs will be solicited by the eDiary in each part except Part 1B: headache, fatigue, myalgia (muscle aches all over the body), arthralgia (aching in several joints), nausea/vomiting, rash, fever, and chills.

The solicited ARs will be graded based on the grading scales presented in [Table 6 in the protocol](#), modified from the Toxicity Grading Scale for Healthy Adult and Adolescent Volunteers Enrolled in Preventative Vaccine Clinical Trials (DHHS 2007). Investigator will assess Grade 4 events (with exception of fever).

If a solicited local or systemic AR continues beyond 7 days post injection, the participant will be prompted to capture solicited local or systemic AR in the eDiary until resolution.

All solicited ARs (local and systemic) will be considered causally related to injection.

Analyses of solicited ARs will be provided by treatment group based on the Solicited Safety Set, unless otherwise specified.

The number and percentage of subjects who reported each individual solicited local AR (has a severity grade of Grade 1 or greater) and solicited systemic AR (has a severity grade of Grade 1 or greater) during the 7-day follow-up period after each injection will be tabulated by vaccination group, severity grade, and injection. The number and percentage of subjects who reported each individual solicited AR will also be summarized by vaccination group, severity grade, days of reporting and injection.

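### The MAAE and AE-discontinuation outputs are limited to unsolicited events, so as written they do not report the full MAAE endpoint and can undercount it

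*SAP*

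**What the plan says.** Part 1A SAP, Section 3.1, lists as a primary safety endpoint "Medically-attended AEs (MAAEs) through the entire study period". In the SAP for Parts 1B, 1C, 2 and 3, Sections 3.2.1, 3.3.1, 3.4.1 and 3.5.1 list MAAEs, also unqualified, as primary safety endpoints. Those four sections add AEs leading to discontinuation or withdrawal from study participation. Part 1A Section 3.1 does not.

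Section 6.3.1 of both SAPs has the investigator assess each AE for "MAAE which is defined as an AE that leads to an unscheduled visit to a healthcare practitioner". Section 6.3.2 of both says "An AR is any AE for which there is a reasonable possibility that the test product caused the AE", and treats every solicited reaction as causally related to injection.

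The planned outputs are narrower. Section 6.3.1.1 of both SAPs has the rows "Any unsolicited medically-attended TEAEs" and "Any unsolicited TEAEs leading to discontinuation from study vaccine", with a matching row for discontinuation from the study. Section 6.3.1.2 repeats the restriction by system organ class and preferred term, for example "All unsolicited TEAEs leading to discontinuation from study vaccine". The MAAE and discontinuation listings carry it too. The serious, fatal and AESI rows do not.

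**The concern.** Reactogenicity is part of the primary safety objective, and reactions that send an adolescent to a practitioner or end participation are among its more informative results. If the endpoint covers all MAAEs but its tables select unsolicited ones, a fever or myalgia in the first seven days that led to a visit may appear in the report only as a graded solicited reaction, with nothing to show that care was sought. The tables of treatment-related MAAEs would then omit a class of events that the SAP treats as related by rule. AE-discontinuation has the same gap, and there it touches a primary endpoint in Parts 1C-1, 1C-2, 2 and 3.

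**Working it through.** No stated sample size, power or alpha is involved. The check sets the SAP's sections side by side.

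1. **Is a medically attended solicited reaction inside the endpoint?** An AR is an AE (6.3.2). One that begins after injection is treatment-emergent (6.3.1). An AE leading to an unscheduled healthcare visit is an MAAE (6.3.1). The endpoint is MAAEs with no exclusion (3.1). The answer is yes.

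2. **Is it inside the MAAE outputs?** The summary row, the two preferred-term tables (all and treatment-related) and the listing all specify unsolicited events (6.3.1.1 and 6.3.1.2, both SAPs). As worded, the answer is no.

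3. **Does another output show it?** Section 6.3.2 of both SAPs tabulates solicited reactions by grade, injection, reporting day, onset and duration. Neither medical attendance nor discontinuation is among these. The answer is no.

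4. **Are such visits foreseeable?** Appendix E, footnote 11, states "An unscheduled visit may be prompted by reactogenicity issues, illness visit criteria for COVID-19, or new or ongoing AEs". This concerns unscheduled visits in the trial. It shows that visits for reactogenicity are expected, but not how often care is sought elsewhere.

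5. **Discontinuation.** Section 6.3 of both SAPs names AEs leading to withdrawal as a safety parameter without limiting them to unsolicited events, while 6.3.1.1 and 6.3.1.2 do limit them. Section 6.2.1 of the Part 1A SAP tabulates reasons for stopping before the second dose and for leaving the study, and adds a listing with reasons. This covers the gap in part, but it does not give an AE-level table.

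6. **Long-term summary.** In the companion SAP (6.1) the long-term safety period starts at the first mRNA-1273 dose in both cohorts. On solicitation, its Section 6.3.2 says "The following systemic ARs will be solicited by the eDiary in each part except Part 1B", and the local reactions have the same exception. A day-2 fever with a visit is then a solicited reaction outside the MAAE row in the mRNA-1273 cohort, but can be an unsolicited MAAE inside it in the crossover cohort. Appendix F records MAAEs from the first open-label dose.

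7. **Size.** The documents give no rate of solicited reactions leading to care or stopping, so nothing can be derived. For illustration, with 2,000 assigned to mRNA-1273 and 1,000 to placebo (Part 1A SAP, 4.1.1.1):
   - Assumed vaccine rates: 2,000 × 0.05% = 1; × 0.1% = 2; × 0.5% = 10; × 1% = 20; × 2% = 40 participants.
   - Assumed placebo rates: 1,000 × 0.1% = 1; × 0.5% = 5 participants.
   - Taking 0.5% to 2% for vaccine and 0.1% to 0.5% for placebo, the omitted risk difference runs from 0.5 − 0.5 = 0 to 2 − 0.1 = 1.9 percentage points. The range includes no effect.

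**The case against.** The strongest reply is that a recording rule in the protocol, which is not shown, may decide the matter: a solicited reaction that leads to care could also be entered by the site as an AE. There are signs of such a route. The investigator assesses MAAEs, they have their own line in the schedule, and Appendix E, footnote 7, asks for clinically significant findings at a visit to be reported as MAAEs just after describing examination of the injected arm and nodes. On this view *unsolicited* is a data-source label. Section 6.3.1.1 introduces its whole list as a summary of unsolicited TEAEs, and Part 1A Section 6.6 groups SAEs and MAAEs together under unsolicited AEs.

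This stands in part. Some attended reactions may well reach the MAAE data. But the outputs would still select unsolicited events, and neither SAP has a rule that reclassifies an attended solicited reaction as unsolicited. If the word is only a source label, the SAP should say so.

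A reader might go further and infer that harm is understated as a matter of fact, or that the vaccine–placebo difference is biased toward zero. The documents do not support that. The reactions are counted and graded, the serious and fatal rows are not worded to exclude them, and neither the frequency nor the arm imbalance of attended reactions is given. A reader might also take the long-term asymmetry for a biased comparison. Section 6.6 of the Part 1A SAP plans no comparison between those cohorts, so the effect is on a descriptive display.

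**Conclusion.** The mismatch between endpoint and outputs is real and lies within the SAP. As written, the MAAE tables do not report all events that the SAP defines as MAAEs, and they can undercount the endpoint. The amount cannot be computed from the documents; the figures under the check rest wholly on assumed rates. Any undercount also depends on how attended solicited reactions were recorded, which the SAP does not settle.

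For discontinuation the point is narrower. It concerns a primary safety endpoint only in Parts 1C-1, 1C-2, 2 and 3. In Part 1A it is not a primary endpoint, and disposition reasons and a listing partly cover it. The long-term inconsistency follows from the same wording and should be settled with it. The change should be made because it is specific and cheap, not because a known bias has been shown.

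**What to change.** In Sections 6.3.1.1 and 6.3.1.2 of both SAPs, add rows, tables and listings for MAAEs, AEs leading to discontinuation from vaccine and AEs leading to discontinuation from the study that cover all TEAEs, solicited or unsolicited, wherever attendance or stopping was recorded. Count each participant once and use the Safety Set. Keep the present unsolicited-only rows as a breakdown. Apply the same all-event rule to both cohorts in the long-term summary. State in 6.3.1 how a solicited reaction meeting the MAAE or discontinuation criterion is classified.

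The cost is SAP wording and a few extra table runs. Because both SAPs specify MedDRA coding for unsolicited AEs, the preferred-term tables also need a mapping for the solicited terms, which form a short fixed list. The reported percentages may become slightly less favourable to the vaccine. If attendance or stopping was not captured for eDiary-only reactions, a rerun cannot recover it, and the report should say so.

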### **6.3.1.2. TEAEs by System Organ Class and Preferred Term**

The following summary tables of TEAEs will be provided by SOC and PT using frequency counts and percentages (i.e., number and percentage of subjects with an event):

- All unsolicited TEAEs
- All unsolicited TEAEs that are treatment-related
- All serious TEAEs
- All serious TEAEs that are treatment-related
- All unsolicited TEAEs leading to discontinuation from study vaccine
- All unsolicited TEAEs leading to discontinuation from participation in the study
- All unsolicited Severe TEAEs
- All unsolicited Severe TEAEs that are treatment-related
- All unsolicited medically-attended TEAEs
- All unsolicited medically-attended TEAEs that are treatment-related
- All AESI of MIS-C
- All AESI other than MIS-C

#### **6.3.1.3. TEAEs by Preferred Term**

A summary table of all unsolicited TEAEs will be provided. PTs will be sorted in a descending order according to the frequency in mRNA-1273 group.

#### **6.3.1.4. TEAEs by System Organ Class, Preferred Term and Severity**

The following summary tables of TEAEs will be provided by SOC, PT, and maximum severity (mild < moderate < severe) using frequency counts and percentages:

- All unsolicited TEAEs
- All unsolicited TEAEs that are treatment-related

#### **6.3.2. Solicited Adverse Reactions**

An AR is any AE for which there is a reasonable possibility that the test product caused the AE. The term “Solicited Adverse Reactions” refers to selected signs and symptoms occurring after injection administration during a specified post-injection follow-up period (day of injection and 6 subsequent days). The solicited ARs are recorded by the subject in eDiary. The occurrence and intensity of selected signs and symptoms is actively solicited

from the participant during a specified post-injection follow-up period (day of injection and 6 subsequent days), using a pre-defined checklist (i.e., solicited ARs).

The following local ARs will be solicited by the eDiary: pain at injection site, erythema (redness) at injection site, swelling (hardness) at injection site, and localized axillary swelling or tenderness ipsilateral to the injection arm.

The following systemic ARs will be solicited by the eDiary: headache, fatigue, myalgia (muscle aches all over the body), arthralgia (aching in several joints), nausea/vomiting, rash, fever, and chills.

The solicited ARs will be graded based on the grading scales presented in [Table 6 in the protocol](#), modified from the Toxicity Grading Scale for Healthy Adult and Adolescent Volunteers Enrolled in Preventative Vaccine Clinical Trials (DHHS 2007). Investigator will assess Grade 4 events (with exception of fever).

If a solicited local or systemic AR continues beyond 7 days post injection, the participant will be prompted to capture the solicited local or systemic AR in the eDiary until resolution.

All solicited ARs (local and systemic) will be considered causally related to injection.

Analyses of solicited ARs will be provided by treatment group for each injection (first or second) based on the associated subset of Solicited Safety Set, i.e. First (Second) Injection Solicited Safety Set; and for any injection based on the Solicited Safety Set, unless otherwise specified.

The number and percentage of subjects who reported each individual solicited local AR (has a severity grade of Grade 1 or greater) and solicited systemic AR (has a severity grade of Grade 1 or greater) during the 7-day follow-up period after each injection will be tabulated by vaccination group, severity grade, and injection. The number and percentage of subjects who reported each individual solicited AR will also be summarized by vaccination group, severity grade, days of reporting and injection.

The number and percentage of subjects experiencing fever (a temperature greater than or equal to 38.0°C/100.4°F by the oral, axillary, or tympanic route) by severity grade will be provided.

A two-sided 95% exact confidence interval (CI) using the Clopper-Pearson method will be provided for the percentage of subjects who reported any solicited local AR, solicited systemic AR, or any solicited AR.

The onset of individual solicited AR is defined as the time point after each injection at which the respective solicited AR first occurred. The number and percentage of subjects with onset of individual solicited AR will be summarized by vaccination group, study day relative to the corresponding injection (Day 1 through Day 7), and injection.

The duration will be calculated as the end date/day of the solicited AR event – the start date/day of the solicited AR event + 1 when the solicited AR is reported within the 7 days of injection. If the solicited AR continues beyond 7 days, the days a solicited AR is reported after 7 days will be included (e.g., an event that lasted 5 days in the first 7 days post injection and 3 days beyond 7 days post injection, the duration will be reported as 8 (5+3) days.)

